3.3. Research Objective, Endpoints and Questions

3.3.1. Research Questions

OPTIMISE study objectives are dual and aim primarily to increase the knowledge regarding the outcomes from SU use on one hand; and outcomes from the combined SU- 2nd line sequence on the other hand in real life clinical practice. This will be addressed in many countries across AfME and in individual country cohorts to understand specificities and differences in use and outcomes.

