6.1. Selection of First-Line Treatment

6.1.1. First-Line Treatment in Patients With Favorable- to Intermediate-Risk Clear Cell mRCC

Currently, Phase III data originating from four randomized trials support the use of three molecules in the first-line setting, ie, Sunitinib,^{5,6} pazopanib,⁷ and bevacizumab, in combination with interferon- α .^{8,9} The criteria for choosing between Sunitinib and pazopanib currently represent the hottest topic of debate. Its importance prompted the design and conduct of the first head-to-head Phase III trial comparing two first-line treatment alternatives for mRCC patients.¹⁰

A head-to-head prospective Phase III trial of Sunitinib and pazopanib [COMPARZ], ClinicalTrials.gov identifier NCT00720941¹⁰ the randomized design rested on the non-inferiority comparative effectiveness of 800 mg once daily continuous dosing of pazopanib relative to 50 mg once daily 4/2 weeks dosing of sunitinib. Although there is no doubt that direct comparison of Sunitinib versus pazopanib represents an effort aimed at providing evidence data in regards to two management alternatives for clear cell mRCC patients, many questions pertaining to study results and their interpretation remain unanswered.

The observation of differences in patterns of care between community and academic practice dovetails with other retrospective reports. Choueiri et al. published a series of 144 RCC patients from two tertiary oncology centers in the US. Patients were treated with Sunitinib, sorafenib, or bevacizumab from 2003 to 2008. Treatment patterns, response rates, and adverse events were described.¹² Similar data were obtained from a retrospective review of 250 patients with mRCC treated at 18 community oncology clinics. Differences in outcomes between these two studies included median duration of first line therapy for both Sunitinib (5.9 months in the community vs. 10.5 months in the academic centers) and sorafenib (5.5 vs. 8.1 months). In addition, patients in the community were more likely to receive lower doses of Sunitinib and sorafenib and were more likely to have dose reductions and interruptions than patient in the academic centers. These differences in practice patterns are an important area of further research and may lead to the understanding of more optimal treatment regimens for patients.¹³

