8.7. Sample Size

Due to the non-existence of a sample size calculation/justification for estimating the median progression free survival in phase IV trials and the exploratory/observatory nature of this study, we opt not to base the sample size on the main objective. However, we will use the secondary objective of estimation of the ORR for adv/mRCC patients receiving SU in the 1st line as the basis of the sample size. With 140 patients we will be able to assess the ORR to within a margin of error of at most $\pm 8\%$ using 95% confidence intervals. This is based on the assumption that the ORR will be less than 37% as per the literature.^{12,25} This sample size is also within the range of sample sizes of other studies investigating SU for first line and where PFS and TTF were estimated.²⁵

The 140 patients will be enrolled at 14 sites in the Middle Eastern & African countries; namely UAE, Qatar, RSA, Egypt, Algeria, Tunisia and Morocco. Each site is expected to enroll an average of 10 patients. This will ensure diverse and possibly representative sample of the Middle East and North Africa region.

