8.9. Data Analysis

Detailed methodology for summary and statistical analyses of data collected in this study will be documented in a Statistical Analysis Plan (SAP), which will be dated, filed and maintained by the sponsor. The SAP may modify the plans outlined in the protocol; any major modifications of primary endpoint definitions or their analyses would be reflected in a protocol amendment.

Demographic and other clinical characteristics of the patients will be summarized using the mean, standard deviation, median, minimum, and maximum values, for numeric variables such as age and duration of follow up and frequency distributions for categorical data such as gender. The median and 95% confidence intervals for the main outcomes PFS and TTF will be estimated using the method of Kaplan-Meier. The ORR for adv/mRCC patients receiving SU in the 1st line will be computed along with its 95% confidence interval using the Clopper-Pearson formula. Cox proportional hazard models may be used to explore the potential influences of baseline characteristics on PFS or TTF. A multiple logistic regression model can be used to assess the effect of prognostic variable on ORR.

Change in other variables such as Quality of life and weight at last visit as compared to the baseline will be assessed using the paired t-test at each visit in addition to computing mean differences along with 95% confidence intervals. Moreover, repeated methods can be used to look for trends over time and adjust for possible confounders.

All AEs occurring during the study will be considered as treatment-emergent, and the frequency of AEs will be summarized. Sub-group analyses of association between efficacy outcomes, safety measurements, and baseline factors will be performed for exploratory reasons as needed.

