7.1. Descriptive methods

- Descriptive analysis of qualitative and ordinal variables will comprise the count and the frequency of each category.

- Descriptive analysis of quantitative variables will be presented by the mean and standard deviation (SD) for the data that follows a Gaussian distribution and the median and range otherwise.
- The 95% confidence intervals will be presented for main endpoints. The ‘exact’ Clopper-Pearson confidence interval will be provided to assess 2-sided 95% confidence interval for main binomial proportions (e.g. ORR rate).
- The number of missing values will be reported in the results table for each variable.

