7.4. Survival analysis methods

- The survival functions for PFS, TTF, TSF, and OS will be estimated with the Kaplan-Meier method. The survival function $S(t)$ is the probability that the event (treatment discontinuation, death or progression) does not occur before a specified time.
- This method will be applied to derive, survival curves, median event time and a 95% confidence interval for the median survival time (time at which half the analyzed patients have presented the event).
- Survival curves will give an idea of whether or not the groups are proportional (i.e. the survival functions are approximately parallel).
- For OS, the share of patients alive at 24 months will also be measured.
- The log-rank test of equality across strata will be used to compare survival curves for categorical variables (sub-groups of interest).
- For continuous variables, a univariate Cox proportional hazard regression will be used.
- For analyses of prognostic factors of survival time, multivariate Cox proportional hazard regressions will be performed.

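### Patients are recruited in about 14 site clusters of about 10, but no readable analysis accounts for site; if outcomes vary between sites, the 95% intervals for PFS, TTF and ORR are too narrow for regional inference

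*Protocol*

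**What the plan says.** Protocol 8.7 places the 140 patients at 14 sites in seven countries: "Each site is expected to enroll an average of 10 patients". It justifies the number through ORR: "With 140 patients we will be able to assess the ORR to within a margin of error of at most" ±8%, and adds "This is based on the assumption that the ORR will be less than 37% as per the literature".

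For the primary endpoints, Protocol 8.9 says: "The median and 95% confidence intervals for the main outcomes PFS and TTF will be estimated using the method of Kaplan-Meier". SAP 7.4 repeats this for PFS, TTF and OS and adds log-rank tests and Cox models. For ORR, SAP 7.1 says a "Clopper-Pearson confidence interval will be provided to assess 2-sided 95% confidence interval for main binomial proportions", and SAP 7.3 adds logistic regression.

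The treating physician sets dose and duration (Protocol 8.2), and monitoring follows that physician's normal practice (Protocol 8.11). SAP 4.1 names AfME patients as the population to which the findings will be carried over. Protocol 3.3.1 also wants to look "in individual country cohorts to understand specificities and differences in use and outcomes".

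No readable passage uses site as a cluster, stratum, random effect or covariate. Neither SAP 5.5 nor SAP Appendix 3 lists site or country. The one model for correlated data, the MMRM for quality of life (SAP 7.5), handles repeated measures within a patient and lists no site effect.

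**The concern.** The sampling has two stages: sites first, then patients within sites. Decisions made at site level bear directly on TTF, which ends on the date the physician stops sunitinib, and on when progression is detected. Patients at one site may therefore resemble each other more than patients at different sites. The usual Kaplan-Meier variance and the Clopper-Pearson interval both assume independent patients. Where outcomes are positively correlated within sites, they overstate how much 140 patients reveal about the region.

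This is a single-cohort descriptive study, so its estimates and their 95% intervals are its main product. At stake is whether those intervals miss the regional value about 1 time in 20, as a reader will assume, or more often.

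**Working it through.** **Inputs from the documents.** n = 140, 14 sites, 10 per site on average, ORR below 37%, margin ±8% (Protocol 8.7); 12 months of accrual and at least 1 year of follow-up (Protocol 8.1); the interval methods above. **Assumed:** an ICC of 0.01 to 0.10, since the documents give none.

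**1. The plan's own figure.** Half-width = 1.96 × √(0.37 × 0.63 / 140) = 0.080, or 8.0 points. In reverse, n = 0.2331 × (1.96 / 0.08)² = 139.9. So 140 and ±8% reproduce, under independence and the normal approximation. The planned exact interval is slightly wider: 52/140 gives 29.1% to 45.7%, a half-width of 8.3 points.

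**2. ORR with clustering.** Design effect (DE) = 1 + (10 − 1) × ICC; effective n = 140 / DE; margin = 8.0 × √DE. The last column is the simulated error rate of Clopper-Pearson at ORR 37% (beta-binomial, 14 sites of 10).

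| ICC | DE | Effective n | Margin (points) | Clopper-Pearson error |
|---|---|---|---|---|
| 0 | 1.00 | 140 | 8.0 | 4.4% |
| 0.01 | 1.09 | 128 | 8.35 | 5.4% |
| 0.02 | 1.18 | 119 | 8.7 | 6.4% |
| 0.05 | 1.45 | 97 | 9.6 | 9.5% |
| 0.10 | 1.90 | 74 | 11.0 | 14.3% |

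The error depends somewhat on the ORR, because the exact interval is conservative by an amount that changes with the rate. At ICC 0.05 it is 7.8% at ORR 36% and 9.1% at ORR 30%. Allowing for this, the error is about 4 to 5% at ICC 0.01, 8 to 9.5% at 0.05 and 12.5 to 14% at 0.10.

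**3. An illustration for TTF.** Protocol 6.1.1 reports median first-line sunitinib duration of "5.9 months in the community vs. 10.5 months in the academic centers". Suppose each site is drawn with equal chance from these two medians, with exponential times.

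- The pooled median is 7.77 months. At that time the proportions still on treatment are 0.5^(7.77/5.9) = 0.401 and 0.5^(7.77/10.5) = 0.599.
- The variance between sites is ((0.599 − 0.401) / 2)² = 0.0098, so the ICC at the median is about 0.0098 / 0.25 = 0.039 and DE = 1 + 9 × 0.039 = 1.35.
- The normal approximation gives an error of 2Φ(−1.96 / √1.35), about 9%.
- Direct simulation of the log-log Kaplan-Meier interval for the median, with censoring at 12 to 24 months, gives about 8%, against about 4% with no site effect.

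**4. Does a clustered interval repair it?** An ORR interval from site-clustered variance on the logit scale, with t on 13 degrees of freedom (2.16 in place of 1.96), covers 95.1 to 95.6% across ICC 0 to 0.10. A delete-one-site jackknife interval for the Kaplan-Meier median covers 95.7% with no site effect and 96.1% under a 50/50 mix of 5.9- and 10.5-month sites.

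**The case against.** **No ICC is given.** A reader might infer that the planned intervals are certainly too narrow. The documents do not support that. It takes a positive ICC, and at 0.01 the conservatism of Clopper-Pearson absorbs the effect. This stands, and the conclusion has to be conditional.

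**The 5.9 and 10.5 months are not site-level evidence.** They come from two separate retrospective studies, one at two tertiary centers and one at 18 community clinics. They concern treatment duration, and case mix or other study differences may explain part of the gap. The documents give no split of the participating sites by practice type. This also stands: the figures are an analogy for TTF and no evidence for PFS or ORR.

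**Country tests.** A reader might infer that the study will test countries against each other at an invalid 5% level. No readable passage plans such a test. Protocol 3.3.1 states a descriptive aim, and the readable part of SAP 4.2.1 lists second-line sequences only. This gives the point no support.

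**Parts of the SAP are redacted or not shown,** and SAP 5.5 calls its covariate list non-exclusive, so the models might include site. That is fair for the models. It does not touch the Kaplan-Meier and Clopper-Pearson intervals, whose defining sections are readable; a covariate in a model leaves them unchanged.

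**Clusters may be smaller than 10.** The efficacy set in SAP 4.1 requires 6 months of follow-up. With 7 per site and ICC 0.05, DE falls to 1 + 6 × 0.05 = 1.30. The effect shrinks but remains.

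**Sites could be treated as fixed.** Inference about these 14 sites alone would not need wider intervals. SAP 4.1 rules out that reading by carrying the results over to AfME patients.

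**The study is hypothesis-generating** (Protocol 8.11), and no decision rests on these intervals. That limits the consequence, but a nominal 95% interval should still cover about 95% of the time.

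**Conclusion.** The point holds in conditional form. The clustered design, the regional inference and the absence of any readable site adjustment are all documented. If outcomes vary between sites, the planned intervals are too narrow for that inference. The size depends on an ICC the documents do not supply: negligible for ORR near 0.01, and material from about 0.05, where the margin is 9.6 points rather than 8 and the error about 8 to 9.5%. The TTF figure (about 8% against 4%) rests on the assumed 50/50 site mix. All figures assume 14 equal sites of 10. At ICC 0.05 and ORR 37%, sites ranging from 2 to 24 patients would raise the Clopper-Pearson error from 9.5% to 11.8%. This is worth correcting because the remedy is cheap; it does not invalidate the planned estimates.

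**What to change.** In Protocol 8.9 and SAP 7.1, 7.3 and 7.4, keep the point estimates and the planned intervals, and pre-specify beside them:

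- **ORR:** a 95% interval from site-clustered variance on the logit scale, with t on (sites − 1) degrees of freedom. Report the observed ICC.
- **PFS, TTF and OS medians:** a 95% interval from a delete-one-site jackknife or an equivalent cluster-robust variance, with the same t.
- **Cox and logistic models:** site-clustered standard errors or a site random effect.
- **Interpretation:** read regional precision from the clustered intervals where the two differ. Report any country differences descriptively, without a p-value.

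The cost is wider intervals and a little programming. For ORR the half-width is about 10.3 points against 8.2 at ICC 0.05, and about 8.6 against 8.25 with no site effect. For the Kaplan-Meier median it is about 2.4 months against 2.0 under the illustrative mix, and 2.0 against 1.9 with no site effect. Enrollment is by site, so no new data are needed. SAP section 7 names SPSS; confirm that these intervals can be produced there, or name the additional software.

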8.5.3. Follow-up Phase

For each subject, after treatment, there would be two follow-up visits (Visit 6-7) in one year, one visit every 6 months (month 18 and 24).

- Concomitant medications (a window period of 28 days prior to the start of the study treatment, during the study and up to 28 days post the last dose of treatment applies).
- Adverse Events Assessment.
- Update in Disease Status (including PFS, RR, TTR, TTF, OS).
- Update in Treatment Status/ Change in therapy.
- Reporting of routine labs collected.

- Performance Status (ECOG), weight (BMI) and blood pressure.
- QOL questionnaire (FKSI 19) ([Appendix 1](#)).

In case of no treatment failure till month 12, more treatment visits will be scheduled until SU discontinuation.

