10.1.2. Reporting Period and Requirements

All adverse drug reactions and other safety information as mentioned below should be documented and reported to Pfizer; for the sake of continuous monitoring of product safety.

Non-AEs and other safety information should be reported to Pfizer, if possible, upon recognition but no later than 10 days.

Patients should be asked to inform the treating physician of any AE or other relevant safety information, immediately. The treating physician has to assess the causal relationship for AEs and report AEs and other relevant drug safety information.

If a SAE occurs that in the opinion of the investigator is related to *Sutent®*, Pfizer is to be notified within 24 hours of awareness of the event and a non-Interventional Study Adverse Event Report Form must be completed and submitted to Pfizer Safety.

In particular, if the serious adverse event is fatal or life-threatening, notification to Pfizer must be made immediately, irrespective of the extent of available adverse event information. This timeframe also applies to additional new information (follow-up) on previously forwarded serious adverse event reports as well as to the initial and follow-up reporting of exposure during pregnancy and exposure during breast feeding and medication error cases.

Suspected adverse reactions that are both serious and unexpected are subject to expedited reporting in accordance with all applicable laws and regulations.

For each patient, the safety event reporting period begins at the time of the patient's informed consent, which is obtained prior to the patient's enrollment in the study, and lasts through the end of the observation period of the study; a report must be submitted to Pfizer Safety (or its designated representative) for any of the types of safety events listed in the table above occurring during this period.

If a patient provides informed consent but is never enrolled in the study (eg, patient changes his/her mind about participation or if patients are screened for eligibility following informed consent, and fail screening criteria), the reporting period ends on the date of the decision to not enroll the patient.

If the investigator becomes aware of a SAE occurring at any time after completion of the study and s/he considers the serious AE to be related to Sutent® (Sunitinib), the SAE also must be reported to Pfizer Safety.

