10.2.2. Serious Adverse Events

A serious adverse event is any untoward medical occurrence in a patient administered a medicinal or nutritional product (including pediatric formulas) at any dose that:

- Results in death;
- Is life-threatening;
- Requires inpatient hospitalization or prolongation of hospitalization (see below for circumstances that do not constitute adverse events);
- Results in persistent or significant disability/incapacity (substantial disruption of the ability to conduct normal life functions);
- Results in congenital anomaly/birth defect.

Progression of the malignancy under study (including signs and symptoms of progression) should not be reported as a serious adverse event unless the outcome is fatal within the safety reporting period. Hospitalization due to signs and symptoms of disease progression should not be reported as a serious adverse event. If the malignancy has a fatal outcome during the study or within the safety reporting period, then the event leading to death must be recorded as an adverse event and as a serious adverse event with severity Grade 5.

Medical and scientific judgment is exercised in determining whether an event is an important medical event. An important medical event may not be immediately life-threatening and/or result in death or hospitalization. However, if it is determined that the event may jeopardize the patient or may require intervention to prevent one of the other outcomes listed in the definition above, the important medical event should be reported as serious.

Examples of such events are intensive treatment in an emergency room or at home for allergic bronchospasm; blood dyscrasias or convulsions that do not result in hospitalization; or development of drug dependency or drug abuse. Additionally, any suspected transmission via a Pfizer product of an infectious agent, pathogenic or non-pathogenic, is considered serious. The event may be suspected from clinical symptoms or laboratory findings indicating an infection in a patient exposed to a Pfizer product. The terms “suspected transmission” and “transmission” are considered synonymous. These cases are considered unexpected and handled as serious expedited cases by PV personnel. Such cases are also considered for reporting as product defects, if appropriate.

Hospitalization

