4.2. Subgroups

4.2.1. Subgroups to meet primary and secondary objectives

- Compare efficacy parameters (PFS, OS) for the combined 1st line SU- 2nd line sequences according to the second line post SU :
 - SU in 1st line-Axitinib TKI in 2nd line
 - SU in 1st line- other TKI in 2nd line (sorafenib, pazopanib)
 - SU in 1st line/mTOR in 2nd line (temsirolimus, everolimus)

CCI [REDACTED]

- [REDACTED]
- [REDACTED]
- [REDACTED]
- [REDACTED]
- [REDACTED]

[figure not shown] 2);

- Incidence of other AEs (grade ≤ 2);
- Incidence of all AE per grade.
- AEs will be analyzed separately for AEs related to SU as solicited and unsolicited AE.
- **Discontinuation due to toxicity**
 - Proportion of patients who discontinued the treatment of interest, because of AEs;
 - Treatment duration until discontinuation for AEs;
- **Deaths**
 - Proportion of patients who died due to any cause, over the treatment period (including the 28 days after the treatment discontinuation) and along the study;
 - Cause of death (tumor-related, other cause).

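### Protocol 8.9 calls every adverse event in the study treatment-emergent, with no start or end tied to sunitinib dosing, so the planned AE table mixes on-sunitinib and later events

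*Protocol*

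**What the plan says.** Protocol 8.9 sets the analysis rule: "All AEs occurring during the study will be considered as treatment-emergent". It does not mention the first or last SU dose.

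Protocol 10.1.2 sets the collection window. For each patient "the safety event reporting period begins at the time of the patient's informed consent", and it "lasts through the end of the observation period of the study". Protocol 8.4.1 and 8.5.3 keep AE assessment at the month 18 and 24 visits, after the treatment phase. Under Protocol 8.1, patients are followed whatever comes after SU: axitinib, another drug or supportive care.

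Two sections narrow what is recorded. Protocol 10.1.1 and 10.3 direct that AEs related to SU go into the eCRF, and 10.3 handles unknown causality as related for reporting purposes. Protocol 10.2.2 works the other way: if the malignancy is fatal, "the event leading to death must be recorded as an adverse event" and as a Grade 5 serious event, with no condition on relatedness.

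In the SAP, section 4.1 builds the safety population from patients with any AE after the first SU dose. The deaths endpoint counts deaths over the treatment period, "including the 28 days after the treatment discontinuation", and also along the whole study, with cause. Table 9.5 is a shell for AEs across the study. It has one Sunitinib heading, divided only by grade.

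**The concern.** A treatment-emergent definition marks which events began while the patient was exposed, or shortly afterwards. A rule that admits every event in the study does not do this. Here the study continues after SU into second-line drugs and supportive care, so the label covers exposed and unexposed time alike.

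Two outputs are at stake. An incidence read from table 9.5 as the experience on SU would include events from after SU had stopped, among them deaths from the cancer. The secondary objective on safety of the SU-then-second-line sequence would have no visible table that separates the second-line period from the first.

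**Working it through.** The plan gives no figure to reproduce on this point. The check is whether the passages fit together.

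| Element | Start | End | Relatedness condition |
|---|---|---|---|
| Treatment-emergent rule (Protocol 8.9) | none given | none given | none |
| Safety reporting (Protocol 10.1.2) | consent | end of observation | mixed |
| eCRF recording (Protocol 10.1.1, 10.3) | not stated | not stated | SU-related; unknown handled as related |
| Fatal malignancy (Protocol 10.2.2) | not tied to dosing | end of study or safety reporting period | none |
| AE definition (Protocol 10.2.1) | product administered | none | none |
| Safety population (SAP 4.1) | after first SU dose | none | none |
| Deaths endpoint (SAP) | treatment period | 28 days after stopping, and also whole study | none; cause tabulated |

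Four kinds of event follow from reading the rows together.

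1. **Malignancy death months after SU.** It is recorded under 10.2.2, treatment-emergent under 8.9, and inside the study-wide scope of table 9.5. That shell shows all grades and Grades 3/4, so a Grade 5 event enters the all-grades count with nothing to mark it as late or disease-related. This is the best-supported case.
2. **Late event judged SU-related or of unknown causality.** It is recorded under 10.1.1 and 10.3 and is treatment-emergent under 8.9, however long after the last dose it began.
3. **Event judged due to a second-line drug.** The recording rule in 10.1.1 and 10.3 would largely keep it out of the eCRF. It does not inflate the SU table, but it is also unavailable for the second-line safety objective.
4. **Pre-dose event.** Enrolment is at SU start (Protocol 8.1), so this interval should be short. The SAP safety population selects patients, not events, so a pre-dose event could still be counted in a patient who also has a later one. This is a minor case.

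SAP tables 9.1 and 9.3 split patients by second-line regimen; table 9.5 does not. SAP 8.2 specifies descriptive methods with no period split.

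**How much observation lies outside SU plus 28 days?** This is an illustration only.

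- Inputs: median first-line SU duration of 5.9 and 10.5 months, from two retrospective series in Protocol 6.1.1. Assumptions: exponential duration, a 24-month horizon H, and a tail g = 28/30.4375 = 0.92 months.
- Mean time on SU plus tail = g + (1 − exp(−λ(H − g)))/λ, with λ = ln 2/median. For 5.9 months, 0.92 + 7.95 = 8.87. For 10.5 months, 0.92 + 11.85 = 12.77.
- Survival is not in the documents. Assume exponential survival with a median of 12 to 30 months. Mean observed time = (1 − exp(−μH))/μ, with μ = ln 2/median: 12.98 months at 12 and 18.42 months at 30.
- Outside share, SU median 5.9: 1 − 8.87/12.98 = 32%, up to 1 − 8.87/18.42 = 52%.
- Outside share, SU median 10.5: 1 − 12.77/12.98 = 2%, up to 1 − 12.77/18.42 = 31%.

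The method is crude. It treats SU duration and survival separately and adds the tail even where SU ended in death. The range of 2% to 52% comes almost entirely from the assumptions.

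**The case against.** The strongest reply is that treatment-emergent is a timing label. Relatedness is assessed separately, and the SAP plans a separate analysis of SU-related AEs. A reader might infer that the plan attributes pre-dose, second-line and disease-death events to SU. The documents do not say that, and the recording rule in Protocol 10.1.1 and 10.3 screens out most events judged unrelated. This stands.

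A second reply is that second-line time is partly meant to be in scope, because safety of the sequence is an objective and SAP 8.2 analyses patients who received it. This also stands, but it argues for showing the periods side by side rather than pooling them.

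Third, the deaths endpoint already gives both a 28-day window and a whole-study count, with cause. That separates late disease deaths in the deaths output, but not in the AE table.

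Fourth, part of the SAP safety-endpoint text is not visible, and Protocol 8.9 lets the SAP modify the protocol's plan. A treatment-emergent window may exist there. The point therefore rests on the protocol rule and the visible shell.

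Finally, a reader might infer that about half or more of the AE data comes from time off SU. Ignoring deaths, the calculation gives 1 − 12.77/24 = 47% to 1 − 8.87/24 = 63%. That is person-time rather than events, it assumes nobody dies, and recorded events are filtered by relatedness. The documents do not support it as a magnitude.

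**Conclusion.** The point holds as a fault in the rule. Followed as written, Protocol 8.9 has no dosing anchor, does not match the start implied by the SAP safety population, and places malignancy deaths and late SU-related or unknown-causality events in the same Sunitinib counts as on-treatment events. It does not hold as a claim that these events are attributed to SU, and the pre-dose part is minor.

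No sample size, estimate or efficacy analysis changes. The number of AEs affected cannot be stated, because survival after SU and event rates by period are not in the documents. The conclusion assumes that no unseen SAP text supplies an AE window. The study is descriptive and hypothesis-generating, which limits the consequences, but a descriptive AE table still has to say which exposure it describes. The change should be made before analysis.

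**What to change.** For analysis, define SU treatment-emergent AEs as those with onset on or after the first SU dose and up to 28 days after the last. This is the window the SAP already uses for deaths.

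Replace table 9.5 with a table by period: on SU plus 28 days; second line, by regimen; and no active treatment. List any pre-dose events separately, and list fatal disease progression separately from other AEs. State how an event is assigned when second-line treatment starts within 28 days of the last SU dose.

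Reconcile the SU-related-only recording rule (Protocol 10.1.1, 10.3) with Protocol 8.9, 10.2.1, 10.2.2 and the second-line safety objective. The table split alone does not meet that objective. If only SU-related AEs are recorded, the second-line columns will be largely empty, and the report should say that second-line safety cannot be fully described.

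The cost is one definition, one revised shell and reconciled wording. AE onset dates and SU start and stop dates are needed, with a stated rule for partial dates. Headline AE counts may fall. Widening what is recorded would add site work; keeping the present rule means accepting the limit on the second-line objective.
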